8. Non-English speaking

Outcome measures

Physical impairment will be determined using objective performance measures of agility (4 step square test and Illinois Agility Test), strength and power (sit to stand test and timed stair ascent), speed (self selected walking speed and 40 yard shuttle run), and postural stability (single leg stance).

Levels of participation will be measured using self reported measures of return to usual major activity (work, active duty, school, home management) and the Paffenbarger Activity Scale (PPAQ) that measures participation in light, moderate and vigorous recreational or sports activities.

Patient reported function and health related quality of life as measured using the total and dimension specific sub scales of the Short Musculoskeletal Functional Assessment (SMFA).

Statistical analysis: We are interested in assessing immediate and long-term improvements in functional performance and self reported outcomes. One-sided paired t-tests will be used to test for improvements in outcomes, comparing baseline data to later outcomes. Differences in means between follow up and baseline will be reported along with 95% confidence intervals.

Analysis of costs and benefits of PRIORITI will include an analysis of costs and outcomes observed over a 12-month period as well as cost-effectiveness projected over the patient lifetime.

Safety monitoring: The Medical Monitor is responsible for monitoring serious adverse events (SAEs) as the study progresses to ensure patient safety. The Medical Monitor may convene a meeting of the DSMB to evaluate any SAEs that he/she determines require immediate attention.

Data Safety and Monitoring Board (DSMB): The DSMB is an independent body responsible for evaluating recruitment, safety and outcome data. The DSMB has the authority to stop the study based on its findings.

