significantly better in the IDEO on all functional measures compared to all other bracing conditions ($p < 0.004$), with the exception of the sit-to-stand five times, in which there was only a significant improvement against the BR ($p = 0.014$). The forty yard dash improved by 37% over the PLS and NONE, and by 28% over the BR. The BR demonstrated a significant improvement in the forty yard dash compared to NONE ($p = 0.033$), and self-selected walking velocity on level terrain over NONE and PLS ($p < 0.028$), but no significant difference was found between the PLS, BR and NONE in any other functional measure. This study did not, however, evaluate the impact on patient reported outcomes of the improvements in functional performance⁴³.

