6.4.1 Primary Endpoints

The primary endpoints are functional performance and self reported functioning as measured using the Short Form Musculoskeletal Assessment (SMFA) and the Veterans Health Survey (VR-12).

Functional Performance The performance test battery includes a dyad of a “less demanding” test and a “more demanding” test for three of the domains. At the study initiation visit, the treating surgeon will clinically evaluate the participant’s health, weight bearing and ambulatory status and will provide written approval in order to proceed with the performance tests. Prior to and during the performance tests, the participant will be reminded that he/she can stop these activities at any point if he/she feels unsafe. Participants in the study will complete the “less demanding” test first and, if the score meets a critical threshold, they will move on to complete the “more demanding” test. This approach will provide information on higher level functioning without risking the safety of those with significant impairment. These dyads are summarized in the table below.

Details of each of these assessments are provided below.

- The Four Square Step Test (FSST)** is a dynamic test of balance and agility. It requires participants to rapidly change direction while stepping forward, backward, and sideways, over a low obstacle⁵⁴. The test has demonstrated reliability and validity through correlation with existing balance tests and a positive predictive value of 86%⁵⁴. The FSST does not require any special equipment and requires little space, and is timed using a stopwatch. Raters place four canes (or piping) in a cross on the floor (all four canes lay flat on the floor). The participant then steps as fast as possible into each square in a designated sequence (see Figure 3).
- The Illinois Agility Test**⁵⁴ is a commonly used test to measure agility by requiring the patient to turn in different directions and at different angles. The test requires the patient to

[figure not shown]

Figure 3: the Four Square Step Test

navigate through a series of cones placed 3.3 meters apart as quickly as possible. It is simple test to administer and requires little equipment. The test is timed using a stopwatch and requires 10 meters of length, 5 meters of width, and 8 cones (or markers of some kind).

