- **10 Meter Shuttle Run (40D):** The 10 meter shuttle run assesses speed. Research staff will measure out a continuous 10 meter stretch that is free of obstacles. This test requires the person to run or walk back and forth between two parallel lines as fast as possible. Patients will start in a standing position and run or walk at their self-selected maximal rate 10 meters and back, for a total of 20 meters. The rater uses a stopwatch to keep time. The Shuttle Run test is easy to administer and requires little equipment and space. Patients are able to run or walk at their own pace, and the test is appropriate for patients at both lower and higher levels of functional ability.
- **Single Leg Stance:** The single leg stance is a measure of postural stability⁶⁶. Participants will be asked to stand with arms crossed and pick one foot off the ground bending the knee to 90 degrees. The rater uses a stopwatch to time how long participants hold this stance up to 60 seconds. This test is done on both legs.

Self -Reported Measures of Function will be assessed at baseline (T0) and at one-year (T4).

Overall Function and Well Being will be measured using two instruments. The Short Musculoskeletal Function Assessment (SMFA) will be used to measure overall function and well being⁶⁷⁻⁶⁸. The SMFA is a shorter version of the 101-item Musculoskeletal Function Assessment (MFA) questionnaire. The SMFA is a 46-item questionnaire consisting of the dysfunction and bother index. The Dysfunction Index includes 34 items for assessing patient function. Subscores for the following 4 domains can be calculated: Daily Activities; Arm and Hand Function; Mobility and Emotional Status. The Bother Index consists of 12 items designed to detect how much patients are bothered by functional items. The SMFA has been evaluated for reliability, validity and responsiveness in patient populations⁶⁷. This scale has been chosen because it is a short, reliable, patient reported assessment of functional status that has been specifically designed for and validated in patients with musculoskeletal conditions, including acute injury⁶⁷⁻⁶⁸.

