10.2 Sample Size Considerations

A total of 85 patients will be consented and enrolled by the military core METRC centers (approximately 25-30 from each center); data collected from these participants will be used to test the research hypotheses.

We anticipate a low dropout rate (<5%) because highly motivated individuals will self-select themselves into the program. We will also provide a modest compensation to participants who are not on active duty for their time and travel. For power calculations we assume we will have complete follow-up data on 80 of the 85 participants who enroll. All functional and satisfaction outcomes are continuous. In Specific Aim 1a and Specific Aims 2a and 2b, we plan to test for improvements in outcomes at a specified point in time after enrollment (8 weeks for Specific Aim 1a and 1 year for Specific Aims 2a and 2b) as compared to baseline. One-sided paired t-tests will be used. Differences in means between follow-up and baseline will be reported along with 95% confidence intervals. The proposed sample size yields 80% power to detect an effect size (mean of the difference in outcomes between follow-up and baseline divided by the standard deviation of the difference) of 0.28 (a modest treatment effect). To put this effect size in perspective, Patzkowski et al., reports effect sizes for FSST, TSA, SSWV-L and 40D of approximately 0.6, 0.7, 1.0 and 1.0, respectively.

Based on the above considerations, the targeted sample size for the study is 85 patients.

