10.6 Analysis Plan

All analyses will be conducted under the supervision of our senior statistician, [name] and METRC's senior economist, [name].

Specific Aims #1 and #2: Assessing Immediate and Long-term Improvements in Functional Performance and Self-Reported Outcomes. As described above, one-sided paired t-tests will be used to test for improvements in outcomes at a specified point in time after enrollment as compared to baseline. Differences in means between follow-up and baseline will be reported along with 95% confidence intervals.

To the extent possible, we will explore how improvement correlates with characteristics of the participants, the type and extent of their injury, baseline measures of impairment, and the percent of pre and post IDEO PT sessions attended (as we expect some variation in adherence to the PT regimen). Differences in improvement will be examined using stratified analyses and regressions where the change in outcomes is the dependent variable. We will also conduct the analysis including and excluding participants who complete less than 1/3 of the PT sessions.

Specific Aim #3: Documenting Patterns of Use and Satisfaction with the IDEO. This aim is largely descriptive in nature. To the extent possible, patterns of use and satisfaction will be compared with other studies reported in the literature. Also, variations in device satisfaction will be modeled as a function of patient characteristics and baseline measures of impairment using the appropriate regression techniques.

Specific Aim #4. Assessing the Economic Impact of PRIORITI. Relative to standard of care (SOC), the PRIORITI program may increase or decrease costs of care. Provision of the IDEO device, the associated rehabilitation program, need for special shoe wear, and any adjustments, repairs or replacements needed during the lifetime of wear represent added costs relative to SOC. However, the PRIORITI program could potentially reduce certain types of resource use and costs relative to SOC. For example, if the IDEO device offers greater mobility (without use of ambulatory aids) or reduced pain, participants might decrease follow-up visits or use of pain medications relative to standard of care. Use of the IDEO could also lead to fewer delayed amputations. Labor force participation, return to duty, and productivity of participants enrolled in

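### Aims 1a, 2a and 2b each rest on several unadjusted one-sided tests, with no stated alpha, rule for meeting the aim, or multiplicity control

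*Combined protocol and SAP*

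**What the plan says.** - **Test.** Section 10.2: "One-sided paired t-tests will be used. Differences in means between follow-up and baseline will be reported along with 95% confidence intervals". Section 10.6 repeats that "one-sided paired t-tests will be used to test for improvements in outcomes at a specified point in time after enrollment", and the Protocol Summary says the same. None of these places gives a significance level or says whether the interval is one- or two-sided.
- **Hypotheses.** The Protocol Summary words each of 1a, 2a and 2b as a single statement of significant improvement over baseline.
- **Primary outcomes.** Section 6.4.1 makes functional performance primary together with "self reported functioning as measured using the Short Form Musculoskeletal Assessment (SMFA) and the Veterans Health Survey (VR-12"). The Protocol Summary instead describes self-reported function "using the total and dimension specific sub scales of the Short Musculoskeletal Functional Assessment" and does not list VR-12. Section 6.4.1 also says "The SMFA is a 46-item questionnaire consisting of the dysfunction and bother index", and adds four domain subscores.
- **Performance battery.** Section 6.3.1 and Appendix C list seven tests, repeated at T2 and T4. For single leg stance, section 6.4.1 says "This test is done on both legs", without naming the leg to be analysed. Three of the seven are harder tests done only conditionally: "if the score meets a critical threshold, they will move on to complete the" harder one.
- **Power.** Section 10.2 assumes 80 complete pairs out of 85 enrolled, and states 80% power at a standardised paired difference of 0.28.

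**The concern.** Seven p-values do not by themselves answer one yes-or-no hypothesis. The plan does not link them, so two analysts who both follow the text could reach different conclusions about the same aim. One might call it met when any test is significant, the other only when all are. Under the first rule the chance of a false claim is well above the nominal level. The power statement has the same gap, because it describes one test and not an aim. The inconsistent outcome list adds to this: until it is settled which SMFA scores count and whether VR-12 is primary, the number of tests for aim 2b is open.

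**Working it through.** **1. Inputs.** From section 10.2: 80 pairs, effect d = 0.28 (mean difference divided by SD of the difference), one-sided paired t-test, 80% power. Alpha is not given and has to be inferred. Correlations between outcomes are not given and are assumed over a range.

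**2. Reproducing the plan's figure.** Power = P(T > t_crit), where T is noncentral t with 79 df and noncentrality 0.28 × √80 = 2.504.

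| One-sided alpha | t_crit | Power at 0.28 | Effect detectable with 80% power |
|---|---|---|---|
| 0.05 | 1.664 | 79.9% | 0.280 |
| 0.025 | 1.990 | 69.6% | 0.317 |
| 0.05/7 = 0.00714 | 2.505 | 50.3% | 0.375 |
| 0.025/7 = 0.00357 | 2.762 | 40.4% | 0.404 |

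Of these levels, only one-sided 0.05 without adjustment gives the stated 80%.

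**3. Count of tests.** Aim 1a: 7 at T2. Aim 2a: 7 at T4. Aim 2b: at least 2 at T4 (one score each for SMFA and VR-12). Total 7 + 7 + 2 = 16 as a minimum.

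**4. False-positive rate if any positive test meets the aim.** This takes all nulls as true and each test at one-sided 0.05. With k independent tests it is 1 − 0.95^k. With a common correlation ρ, using normal test statistics, it is 1 − ∫ φ(u) Φ((1.645 − √ρ·u)/√(1 − ρ))^k du.

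| ρ (assumed) | k = 7 (aim 1a or 2a) | k = 2 (aim 2b, minimum) |
|---|---|---|
| 0 | 30.2% | 9.8% |
| 0.3 | 24.5% | 9.3% |
| 0.5 | 20.3% | 8.8% |
| 0.7 | 15.9% | 8.0% |
| 0.9 | 10.5% | 6.8% |

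**5. What Holm does.** Holm keeps each aim's error at or below the family level. In 10,000 simulated trials per setting, with seven true nulls and family 0.05, the error was 4.6% at ρ = 0.3, falling to 2.1% at ρ = 0.9. The strictest step over seven tests has the detectable effects in step 2: 0.375 (family 0.05) or 0.404 (family 0.025). For two scores the strictest step is 0.05/2 = 0.025 or 0.025/2 = 0.0125, with detectable effects 0.317 or 0.350. At an effect of 0.6, power at the strictest seven-test step is above 99% with 80 pairs.

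**6. Interval and test.** If the 95% interval is two-sided (an assumption), it corresponds to one-sided 0.025. The share of trials that are significant at one-sided 0.05 but have an interval including no change is power(0.05) − power(0.025). That is 79.9% − 69.6% = 10.3% at effect 0.28, 97.1% − 94.2% = 2.9% at 0.4, and 0.03% at 0.6.

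**The case against.** The strongest reply is that this is a single-arm before-after study that reports every mean difference with an interval, so readers can judge the pattern for themselves. The outcomes are also correlated, and the effects cited in section 10.2 (about 0.6 to 1.0) are so large that adjustment would hardly matter. Part of this stands. Large effects do survive Holm, and correlation lowers the error. But at a correlation of 0.9 the any-positive rate is still about 10% for seven tests, and a large effect does not supply a missing rule. The cited effects cover four performance tests only. Of the earlier brace comparison, section 2.1 says: "This study did not, however, evaluate the impact on patient reported outcomes". They give no reassurance for aim 2b.

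A second reply is that the documents never write out one test per measure. That is correct: sections 10.2 and 10.6 speak only of testing for improvements in outcomes. The count of 16 is an inference from the absence of any composite or global test.

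A reader might also count single leg stance twice, along with every SMFA score. The documents do not support a firm higher count. Inclusion requires a unilateral injury, and the exclusion criteria protect a healthy control limb, so the uninjured leg is most naturally a comparator. The SMFA list itself is unsettled.

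**Conclusion.** The gap is real and worth closing before analysis. Alpha, the rule for meeting each aim, and multiplicity control are all missing, and the 80% power applies to one unadjusted test at an inferred one-sided 0.05. If any positive test is enough, a performance aim has a false-positive rate of about 30% under independence, and about 25% to 10% at correlations of 0.3 to 0.9. For aim 2b with two scores it is about 10% to 7%. These figures rest on one test per measure, the inferred alpha and assumed common correlations.

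Three stronger readings do not follow.
- **That the study is too small.** The 0.28 is the effect detectable with 80% power, not the expected effect. No rule requiring every test to be positive is stated, and under such a rule error would not exceed 5%.
- **That the interval contradicts the test.** The interval's sidedness is not given. Even a two-sided interval beside a one-sided test is only a mismatch, and it rarely matters at larger effects.
- **That the study-wide error is 1 − 0.95^16 = 56%.** This needs 16 independent tests, while the same patients repeat the same battery at T2 and T4.

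Multiplicity control does not deal with change unrelated to treatment in a before-after design.

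**What to change.** In sections 10.2 and 10.6:

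1. Reconcile the Protocol Summary with section 6.4.1. State which SMFA scores are primary, whether VR-12 is primary, and which leg is analysed for single leg stance.
2. Use Holm-adjusted p-values within each aim. State that the aim is met if at least one outcome is significant after adjustment, or give a stricter rule if the sponsor prefers one. Declare the three aims as separate hypotheses, and say that study-wide error is then not held at the per-aim level. With independent aims it would be 1 − 0.95³ = 14%, or 1 − 0.975³ = 7%.
3. State alpha. Say that 80% power at 0.28 refers to one unadjusted test at one-sided 0.05. Give the strictest-step detectable effect over seven tests beside it: 0.375 (family 0.05) or 0.404 (family 0.025) with 80 pairs. Note that it is larger for the three conditional tests if they have fewer pairs.
4. Minor, and only if the 95% interval is two-sided: match it to the test. Either use one-sided 0.025 (single-test detectable effect 0.32), or keep 0.05 and report 90% intervals or one-sided 95% bounds.

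**Cost.** This is text only and needs no extra patients, provided the sponsor accepts the larger detectable effect per outcome. Keeping 80% power at 0.28 for a single outcome at the strictest step would need 142 pairs (family 0.05) or 163 (family 0.025). For the aim as a whole the loss is smaller. If all seven effects are 0.28 with 80 pairs, the simulated chance of at least one Holm-significant outcome at correlations 0.3, 0.5, 0.7 and 0.9 is 94%, 88%, 80% and 67% (family 0.05), or 89%, 81%, 72% and 57% (family 0.025).

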10.3 Randomization

N/A

10.4 Missing Data and Measures to Minimize Bias

Missing data is a serious concern that complicates the interpretation of the study results. We will address this issue from both a study conduct and analysis perspective. Regarding study conduct, we will:

1. Limit participant burden and inconvenience in data collection
2. Select high quality investigators
3. Provide pre-study training of investigators as well as on-study reinforcement
4. Reimburse investigators based on follow-ups completed not on per-patient basis.
5. Monitor and report missing data rates during the study
6. Emphasize the importance of full participation in the study during the consent process.
7. Collect information on the reasons for missing data.
8. Actively engage participants and educate them about the importance of participation
9. Hold regular Protocol Committee meetings to discuss strategies for follow-up
10. Set targets for acceptable rates of missing data and terminate sites not meeting targets.

While these efforts will help to minimize missing data, we recognize that missing data is inevitable. With this in mind, we will conduct sensitivity analyses to evaluate the robustness of the study results to various untestable assumptions about the missing data mechanism. In addition to unadjusted analyses, which rely on the missing completely at random assumption (testable), we will also estimate treatment effects (utilizing relevant auxiliary information) under the missing at random assumption. Further, we will explore the effect of departures from the missing at random assumption using pattern-mixture and selection modeling techniques.

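### The one-year tests use only people with both T0 and T4, so interim values already collected on people who miss T4 stay out of the main result

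*Combined protocol and SAP*

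**What the plan says.** Section 10.6 (Analysis Plan) sets the test for Aims 1 and 2: "one-sided paired t-tests will be used to test for improvements in outcomes at a specified point in time after enrollment as compared to baseline". Section 10.2 (Sample Size Considerations) powers these tests on complete pairs: "For power calculations we assume we will have complete follow-up data on 80 of the 85 participants who enroll".

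Section 10.4 (Missing Data and Measures to Minimize Bias) describes the analyses for missing data: "In addition to unadjusted analyses, which rely on the missing completely at random assumption (testable), we will also estimate treatment effects", the latter "utilizing relevant auxiliary information) under the missing at random assumption". It then adds pattern-mixture and selection models for departures from MAR. All of this is introduced as sensitivity analysis. No MAR model is specified, no auxiliary variable is listed, and T2 and T3 values are not mentioned.

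The data schedule (sections 6.2.2, 6.2.3, 6.3.1, the T3 and T4 interview lists in 6.3, and Appendix C) gives three time points for each outcome:

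- Performance tests: T0, T2 and T4.
- SMFA and VR-12: T0, T3 and T4.

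Performance at T2 is also the endpoint of Aim 1a.

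**The concern.** Section 10.6 does not use the word unadjusted, but its paired t-tests are evidently the unadjusted analyses of section 10.4. For the one-year aims, a participant who misses T4 contributes nothing to the deciding test, even with an interim measurement of the same outcome on file. The resulting mean change is unbiased only if missing T4 is unrelated to outcome.

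The plan gives reasons to doubt that. It expects low dropout "We anticipate a low dropout rate (<5%) because highly motivated individuals will self-select themselves into the program"'s author-stated reason being motivation, which links retention to a trait likely to track benefit. Section 8.9 allows removal for non-adherence. Section 10.6 expects physical therapy attendance to vary and plans to relate it to improvement.

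With no control arm, dropout bias cannot cancel between groups. It passes directly into the estimated one-year benefit.

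Calling MCAR *testable* could reassure a reader more than it should. Observed data can contradict MCAR but never establish it, and with few losses they will seldom contradict it.

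**Working it through.** **1. The plan's own figure.** Inputs from section 10.2: 80 complete pairs, effect size 0.28 (mean change / SD of change), one-sided paired t-test. Alpha is not stated; 0.05 one-sided is assumed.

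- Noncentrality: 0.28 × √80 = 2.504.
- Critical t, 79 df: 1.664.
- Power (noncentral t): 79.9%, which reproduces the stated 80%. At one-sided 0.025 it would be 69.6%.

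Planned loss: 5/85 = 5.9%.

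**2. Size of a complete-pair bias.** The mean over retained participants exceeds the mean over everyone by

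bias = (fraction missing) × (mean change in retained − mean change in lost).

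With 5 of 85 missing, a gap of 0.5 SD gives 0.0588 × 0.5 = 0.029 SD, and a gap of 0.8 SD gives 0.047 SD. With 17 of 85 missing, the same gaps give 0.10 and 0.16 SD.

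**3. Simulation of the mechanism.** All inputs below are assumptions, because the documents give no correlations or dropout model.

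- Interim change x ~ N(0, 1).
- One-year change y = 0.28 + 0.6x + √(1 − 0.36)·e, with e ~ N(0, 1).
- logit P(T4 missing) = a + bx, with b = −1 or −1.5, that is, odds ratios e^1 = 2.7 and e^1.5 = 4.5 per SD lower interim change; a is set to give the loss rate.
- Complete-pair estimate: mean of y in those with T4.
- MAR estimate: regress y on x in those with T4, then predict at the mean x of all 85.

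| Loss | Complete-pair bias (SD of change) | As share of 0.28 | MAR bias |
|---|---|---|---|
| 5.9% | 0.03 to 0.05 | 11 to 18% | at most 0.003 |
| 10% | 0.05 to 0.07 | 18 to 25% | at most 0.003 |
| 20% | 0.10 to 0.14 | 36 to 50% | at most 0.003 |

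The two estimates have nearly equal standard errors, about 0.11 to 0.12. A second set-up (fixed numbers lost, interim-to-T4 correlation 0.5 to 0.7, dropout correlated 0.5 with interim change) gives complete-pair bias of 0.03 to 0.04 with 5 lost, 0.05 to 0.07 with 9 and 0.09 to 0.12 with 17.

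**4. Where the MAR estimate helps less** (5.9% loss, same slopes).

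- Half of those lost also lack the interim value: MAR bias is about 0.02.
- All of them lack it: MAR bias equals complete-pair bias.
- Dropout depends on the T4 change itself: complete-pair bias is about 0.05 to 0.08 and MAR bias about 0.035 to 0.05, so roughly two thirds remains.

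**5. What a check of MCAR could detect.** Compare one baseline variable between completers and non-completers, two-sided 5%, with noncentrality d·√(n₁n₂/(n₁+n₂)). With 5 against 80, √(400/85) = 2.169 and the critical t (83 df) is 1.989.

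- d = 0.5: noncentrality 1.08, power 19%.
- d = 0.8: noncentrality 1.74, power 40%.
- 80% power needs d of about 1.3.

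With 17 against 68, power is 45% and 83%.

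**The case against.** The strongest reply is that most of the remedy is already planned. Section 10.4 commits to MAR estimates with auxiliary information and to models for departures from MAR, and the interim values are obvious auxiliary information. That stands. What remains is which analysis decides the aim, and that the MAR model is unnamed.

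The plan also works to limit losses. It pays travel for the 12-month visit, sets missing-data targets for sites, and asks for the T4 procedures at an early termination visit where possible (section 6.3.6). These measures should reduce missing data. However, the plan does not say whether early-termination values count as T4.

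At planned retention the bias is under half a standard error (0.05/0.11 = 0.45). That also stands. The larger figures need losses more than three times the plan's 5.9%.

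Some stronger readings are tempting, but the documents do not support them:

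- A reader might infer that the plan rests on a test of MCAR. No such test is named or used; there is one word in parentheses. The low power applies to any check someone might run.
- A reader might infer that T2 and T3 data are discarded. T2 performance is tested in Aim 1a. The gap concerns only the one-year tests, and only T2 for performance and T3 for SMFA and VR-12.
- A reader might infer that the response of someone who misses T4 is largely known. At a correlation of 0.6 the interim change explains 36% of the variance (0.6²).

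**Conclusion.** The point holds for Aims 2a and 2b. Their deciding tests leave out available interim measurements, and the analysis that could use them is secondary and unspecified. Under the assumed correlation and dropout odds ratios, the one-year gain is overstated by about 0.03 to 0.05 SD at planned loss and 0.10 to 0.14 SD at 20% loss. A MAR estimate removes this when the interim value is observed and dropout depends on it; otherwise it removes only part, or none if those lost have no interim value.

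This does not show that the one-year result will be materially wrong if retention goes as planned. It is a better method available at no cost, and it protects against higher losses. The word *testable* is a matter of wording.

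**What to change.** In sections 10.4 and 10.6:

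- For Aims 2a and 2b, make the primary estimate the T4-T0 contrast from a repeated-measures model with a separate mean per visit and unstructured covariance. Include everyone with T0, using T0/T2/T4 for performance and T0/T3/T4 for SMFA and VR-12.
- Keep the paired t-test as supportive, and keep the planned pattern-mixture and selection models.
- Name any further auxiliary variables, and state whether early-termination measurements count as T4.
- Replace the *testable* label with a statement that observed data can refute MCAR but not confirm it, and that with about 5 losses a check has low power.

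The cost is wording only. With complete data the model gives the same mean difference and standard error as the paired t-test.

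One source of missing values is not solved by this change. Section 6.4.1 offers the more demanding tests only to people who reach a threshold on the easier one. Missing values that arise from that rule depend on another test and may reflect inability, so they need their own stated handling.
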